4.2.2 PUK-GHB02: sleep and memory

Following screening procedures prior to enrollment into the experiment, 20 male healthy subjects will be assessed with an actiwatch (for two weeks), questionnaires (Eigenschaftswörterliste [EWL-60], Epworth Sleepiness Scale [ESS], Alcohol Use Identification test [AUDIT], Pittsburgh Sleep Quality Index, Morning Questionnaire [MQ], Positive and Negative Affect Schedule [PANAS], Visual Analog Mood Scale [VAMS], Evening Questionnaire [EQ], Karolinska Sleepiness Scale [KSS], Beck Depression Inventory [BDI], Persönlichkeitsfragebogen, State-Trait Anxiety Inventory [STAI], Mehrfach-Wortschatz-Intelligenztest [MWT-B], Symptomcheckliste 90 [SCL-90]), cognitive tests (Random Number Generation Task [RNG], IOWA Gambling Task [IGT], Psychomotor Vigilance Task [PVT], Delay Discounting Task [DDT]), tests of procedural and declarative memory consolidation (Learning of Texts Task [LTT], Two-Dimensional Object-Location Memory Task [2D-OLMT], Walker Finger Sequence-Tapping Task [FS TT], Paired Associate Word List [PÄWL]), polysomnography (electroencephalography [EEG], electromyography [EMG] and pulse oxymetry), magnetic resonance spectroscopy with electroencephalography (MRS/EEG), functional magnetic resonance imaging with electroencephalography (fMRI-EEG), saliva cortisol, and blood tests (IL-beta, IL-6, IL-10, TNF-alpha, CRP, IL-4, IL-18 und IFN-gamma, tryptophan, kynurenin, kynureninic acid, neopterin, malondialdehyd, qinolinsäure,IDO (indolamine-2,3-deoxygenase), substance P, cortisol, progesterone, BDNF, FMRP, genetic markers, prolaktin) after two applications of GHB (50 mg/kg p.o. vs. placebo – cross over design). Each subject will pass through 7 study nights: one screening night, two adaptation nights and four experimental nights (GHB vs. placebo) (see chart 1). The screening night will take place before the first experimental session. The two first experimental nights will be preceded by one adaptation night. The experimental nights 1+2 will take place in the sleep laboratory of the University of Zurich in collaboration with [name]. The experimental nights 3+4 will take place in the magnetic resonance imaging center (MRZ) of the Psychiatric Hospital of the University of Zurich. The assessment will follow the Good Clinical Practice (GCP) guidelines. Memory testing consists of two steps. First, learning tasks are performed prior to sleep. Second, recalling tasks are performed one hour after awakening. Blood tests for neuroendocrinologic, pharmacokinetic, and depression and sleep biomarker measures will be taken 18 times in total (adaptation nights 6x, experimental nights 6x, post-experimental-night evenings 2x, MRS-fMRI/EEG-nights 4x). Further pharmacokinetic samples will be taken as follows: five hair samples (T0: before testing, T1: days post-experimental night I, T2: seven days post-experimental night I, T3: two days post-experimental night II, T4: six weeks post-experimental night I, T5: before experimental night III, T6: the day after experimental night

III, T7: the day after experimental night IV), seven sweat samples (one sweat patch per night), four urine samples (after every adaptation and experimental night), nine nail samples (weekly nail clipping). A total amount of blood of 250 ml will be taken during the whole experiment GHBO2. The experiment is monitored and all blood drawings are conducted by a medical professional or study nurse. In case of any unexpected incidence threatening the subject's health or if the subject wishes to abandon the study, the procedure will be stopped immediately. All participants will provide urine for a drug screening and absolute exhalative alcohol testing to control for current alcohol and drug use. Any drug use pattern will be assessed using the Interview for Psychotropic Drug Consumption (Quednow et al., 2004). Screening of all subjects includes a daytime screening examination and screening-night in the sleep laboratory, to exclude the inability to sleep in an unknown environment and the presence of specific sleep disorders (e.g. sleep-related breathing disorders, leg movements during sleep). Subjects will receive 800 CHF for participating in the study, plus additional 100 CHF for the hair samples on T4, and another optional 50 CHF for the nail samples.

4.3 Neurocognition, Multiple Sleep Latency and Brain Activity Assessments

4.3.1 Neuropsychological testing

The Cambridge Neuropsychological Test Automated Battery (CANTAB) is a classical neuropsychological test battery measuring visual memory, attention, working memory, executive function and planning. The test batteries begin with simple tests, progressing to more complex tests with repeated test elements. The tests are administered using a computer with a touch-sensitive screen and a tool for reaction timing. CANTAB has been proposed for the assessment of neurotoxic effects (Fray and Robbins, 1996). These tasks are already available in our laboratory and will be applied according to standard procedures.

4.3.2 Tests of sexual arousal and social cognition

The Sexual Arousal Task (SAT), the Multifaceted Empathy Test (MET), the Movie for the Assessment of Social Cognition (MASC) and the Social Gaze Test (SGT) will be used to measure sexual arousal, emotion perception, empathy, and joined attention.

The Sexual Arousal Task (SAT) was designed to investigate the sexual arousal state of the participants. It is based on 15 images from the International Affective Picture System (IAPS), comprising neutral objects, neutral female portraits, neutral couple pictures and explicitly erotic single and couple pictures. In the first part of the task, subjects are shown these pictures in a randomized order, whereas the short presentation time (1 s per image) can be elongated by mouse clicking in a high frequency, if the participants like the picture. This "effort condition", allows measuring difference in the effort of the subjects to see pictures with different degree of arousal content. In the second part of the task, the subjects are asked to rate how "pleasant", "erotic", "attractive", "likeable" and "exciting" they felt about the picture.

The Multifaceted Empathy Test is a photo-based measure to assess empathy in a multidimensional way. It is designed to measure cognitive and emotional empathy simultaneously. The MET consists of a series of photographs, showing people in emotionally charged situations. To assess cognitive empathy, subjects are asked to determine the mental states of the individuals depicted in the photographs. Emotional empathy is assessed by measuring the emotional reactions in response to the pictures. In the Social Gaze Test (SGT), participants are gazed by virtual characters or observe them looking at someone else. In dynamic animations, virtual characters then exhibit socially relevant facial expressions or arbitrary facial movements. Joined attention can be measured by duration of eye contact and interaction with the virtual character. It was shown that the perception of socially relevant facial expressions selectively activates the ventral MPFC. These tasks are already available in our laboratory and will be applied according to standard procedures.

4.3.3 Neuroeconomical testing

We will perform the Social Value Orientation (SVO), Charity Donation (CD) and Reciprocity Task (RT) to assess changes in neuroeconomical reactions under the influence of the drug.

The Reciprocity Task is a monetary distribution task, which is used to investigate the social behavior between two participants. Out of time and infrastructural reason, it is not possible to conduct an interaction between various subjects. That's why a cover story had to be used to create a reliable social interaction condition. So, the subjects are told that they were interacting with other study participants, whereas they interacted just with virtual participants.

The task consists of five interactions with five virtual participants. In each interaction the subject is asked to distribute a value between 0 - 8.- CHF between himself and the opposite (virtual) participant. This task allows to a certain extent to measure the degree of altruism in a monetary distribution situation.

In the Charity Donation Task, participants are given the possibility to donate a value between 0-40.- CHF of their own monetary participant compensation to one of ten listed charity organizations. After that the subjects are asked to rate how pleased they felt about their donation. The participants are further informed that only one of both donations of the two main testing sessions would randomly be chosen to be paid out. The Social Value Orientation (SVO) is another monetary distribution test, which is used to characterize the social behavior of a subject. It allows assigning the subjects to either an altruistic, prosocial, individualistic or competitive category.

We use a SVO version composed of 15 different decision scales. The subjects are instructed to choose for each scale the preferred monetary distribution. They are further told that their decision would directly affect their one final monetary participant compensation (You receive) and the one of the next participant of the study (other receives).

4.3.4 Cognitive and memory testing

Six tasks are used in our study for the assessment of the effects of GHB on nocturnal memory consolidation. The Paired-Associate Word List (PAWL) consists of 46 pairs of nouns, which are presented sequentially on a computer screen. Testing occurs through a cued-recall procedure one time immediately after learning and one time after nocturnal sleep. Memory function is determined by the percentage of recalled matching words (Marshall et al., 2006). The Walker Finger Sequence-Tapping Task (FSTT) is a test of procedural memory, requiring to repeatedly finger-tap with the non-dominant left hand a 5-element sequence presented on a computer monitor. A training period with twelve 30-s intervals is performed anterior to the sleep period. Retrieval testing after sleep consists of a practice run followed by three 30-s test intervals. Performance is determined by the number of correctly completed sequences/30-s Interval (Walker et al., 2002). Moreover, we will implement the following tasks: the Random Generation Task (RNG) assesses executive functions such as inhibition, updating, and monitoring by requiring the participant to randomly name numbers between 1-10 over a defined period of time (Towse and Neil, 1998). In the Iowa Gambling Task (IGT), participants make a series of choices from four decks of cards and receive a reward and/or a loss. "Bad" decks have large rewards but periodically large losses while "good" decks have small but steady rewards and lead to higher payouts overall. Participants must learn the magnitude and probability of rewards from accumulating experience over trials, and over time many healthy participants learn to favor the good decks. Poor performance on this task, on the other hand, is commonly linked to a failure to properly weigh the long-term consequences of choices, such that large losses are neglected in favor of chasing large rewards (Bechara et al., 1994). The Psychomotor Vigilance Task (PVT) is a 10-min lasting test, where subjects have to response to the appearance of a stimulus on a computer screen with pressing a button as fast as possible. It is widely used to assess neurocognitive consequences of sleep loss and circadian misalignment (Basner et al., 2015). The Delay Discounting Task is a paper and pencil test which assesses if subjects tend to choose less reward immediately or higher

reward after a time delay, and it is used to assess impulsive behavior and is sensitive towards sleep deprivation (Kirby et al., 1999).

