4.7.2 Blinding procedure

Blinding will occur through a clinical staff member not involved otherwise in the study. This person will randomly abstract GHB (Xyrem) or placebo (0.9% saline solution) for each subject and put it into a plastic cup with 150 ml standard orange juice using a ml-syringe. In the first experiment (SocCog) sixteen subjects will receive 20 mg/kg and sixteen subjects 35 mg/kg GHB on one occasion and placebo on the other. For the MR-sessions, the same thirty-two subjects will receive 35 mg/kg GHB in one, placebo in the other session in a double-blind, randomized manner. In the second experiment 20 subjects will receive 50 mg/kg GHB on two occasions and placebo on two others. The information about the weight of the subject is transmitted anterior to this procedure. The cup is labeled with the study-code and will be kept back until the end of the study. When the cup is filled, it will be given to the principal investigator, who hands it out to the subject. The subject drinks the whole content and returns the empty cup to the principal investigator.

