23:47	Karolinska Drowsiness Test	2 min
23:50	Waking EEG	10 min
23:55	Blood sample 2 (Venflon; 2 EDTA, Protein, Kalium-Fluorid, Heparin-Plasma, 2 PAX)	5 min
00:00	SLEEP	420 min
08:00	CAR Saliva 1	
	Blood sample 3 (Venflon; 2 EDTA, Protein, Kalium-Fluorid, Heparin-Plasma, 2 PAX)	10 min
08:10	Karolinska Drowsiness Test	5 min
08:15	CAR Saliva 2	
	Morning questionnaire (MQ)	5 min
08:20	Waking EEG	10 min
08:30	CAR Saliva 3	
	EEG/PSG deconnection	10 min
08:40	Urine sample 2	10 min
08:45	CAR Saliva 4	
08:50	Paired Word List Task 2	40 min
09:30	CAR Saliva 5	
09:35	Walker 2	10 min
09:45	IOWA Gambling Task (IGT)	20 min
10:05	Random Number Generation Task (RNG)	10 min
10:15	Psychomotor Vigilance Task incl. SSS	10 min

10:25	Delay discounting task	5 min
10:30	STAI-X1, PANAS, EWL-60, EQ, VAMS	20 min
10:50	Duschen etc.	
	End of Session	

Post Acute Measurement 2		
Time point	Task	Time
12:00 (t12h)	PANAS, EWL-60, VAMS	
16:00 (t16h)	PANAS, EWL-60, VAMS	
19:45	Empfang	
20:00 (t24h)	PANAS, EWL-60, VAMS	
	Blood sample 4 (Venflon; 2 EDTA, Protein, Kalium-Fluorid, Heparin-Plasma, 2 PAX)	
	Nail sample 2	

Time point	Sample	Time
Screening night	Nail sample 1	
Adapt night 1	Hair sample 1	
Post akut 1	Nail sample 2	
Adapt night 2	Hair sample 2	
Post akut 2	Nail sample 3	
2 days post EN 2	Hair sample 3	
2 weeks post EN 2	Nail sample 4 (at home)	
3 weeks post EN 2	Nail sample 5 (at home)	
4 weeks post EN 2	Nail sample 6 (at home)	
5 weeks post EN 2	Hair sample 4	
	Nail sample 7	
6 weeks post EN 2	Nail sample 8 (at home)	
7 weeks post	Nail sample 9 (at home)	

EN 2		
8 weeks post EN 2	Nail sample 10 (at home)	
9 weeks post EN 2	Nail sample 11 (at home)	
10 weeks post EN 2	Nail sample 12 (at home)	
11 weeks post EN 2	Nail sample 13 (at home)	
12 weeks post EN 2	Nail sample 14 (at home)	
13 weeks post EN 2	Nail sample 15 (at home)	
14 weeks post EN 2	Nail sample 16 (at home)	

Experimental night 3		
Zeit (geplant)	Task	Time
21:15	Empfang	
21:30	Drug/Alcohol test	
21:55	Blood sugar measurement	
22:00	Light meal (optional)	
22:15	MR-Fragebogen, VAS, PANAS, VAMS, EQ	
22:20	EEG/PSG installation	
	Sweatpatch 5	
23:00	MRI Baseline	
	Anatomisches MRI	
	MRS	
	Resting Sate fMRI	
23:30	***GHB or Placebo***	
00:00	Blood Sample 1 (Butterfly; 2 EDTA)	
00:05	MRI Session 1	
	Anatomisches MRI	
	MRS NAcc, ACC, Amygdala	
	Resting Sate fMRI	
01:40	Blood Sample 2 (Butterfly; 2 EDTA)	
01:45	VAS, PANAS, VAMS	
	Abend Toilette	
	EEG/PSG connection	
01:50	Karolinska Drowsiness Test	

02:00	Waking EEG	
	Sleep	

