8.2 Number of subjects

Comparable studies to the effects of GHB and other challenges on neuroendocrine and cognitive parameters in awake and sleeping subjects (Carter et al., 2009a, Dumont et al., 2009, Grove-White and Kelman, 1971, Marshall et al., 2006) revealed effect sizes of $d=0.7-1.2$. With a conservative assumption of $d=0.7$, an α -error probability of 5%, and a power of 80% (two-tailed), we would need at least 19 subjects to detect significant differences in each experiment.

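### Four repeated tasks are each described with a single stimulus set, with no parallel forms and no period term, so the second crossover session partly tests remembered material

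*Combined protocol and SAP*

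**What the plan says.** Section 4.3.4 describes one stimulus set per learning task. The word list "consists of 46 pairs of nouns, which are presented sequentially on a computer screen", with cued recall straight after learning and again after sleep, scored as the percentage recalled. The finger-tapping task uses one 5-element sequence. The gambling task uses four decks, and "Participants must learn the magnitude and probability of rewards from accumulating experience over trials".

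In the 6.2 flow chart, experimental nights 1 and 2 carry the same entries for these tasks: word-list learning at 22:05, tapping at 22:45, dosing at 23:30, then "08:50 Paired Word List Task 2" the next morning, followed by tapping and the gambling task. The suffixes 1 and 2 mark evening and morning, because both nights carry both. Nights 3 and 4 do not repeat these tasks.

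For the Sexual Arousal Task (SAT), 4.3.2 says "It is based on 15 images from the International Affective Picture System (IAPS"). The order of the images is randomised, but no second set is described. Table 4 in 6.1 schedules the task on days 1+2 and again as a scan task on days 3+4.

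Sections 4.7.1 and 4.7.2 describe a randomised crossover without stating balanced sequences. Section 8.3 plans repeated-measures ANOVA for every variable and names no period or sequence term. Memory consolidation is among the primary outcome measures in 4.1, and 3.1.2 expects GHB to improve declarative consolidation.

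**The concern.** A crossover relies on each man returning to his starting state between periods. For a drug effect, a long enough gap can secure that. Remembered word pairs, a trained tapping sequence or knowledge of which decks lose money do not wash out with the drug.

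Three separate things can then go wrong:

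- **Ceiling.** Pairs already learned leave less room for any treatment difference in recall.
- **Practice shared by both sequences.** It adds variance to the paired difference if period is not modelled. If the sequences are also unequal, it biases the estimate.
- **Carry-over that depends on the first treatment.** If GHB improves retention, the GHB-first men bring better-retained pairs to their placebo night. Neither balanced order nor a period term removes this.

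For the SAT and the gambling task, the second of these is the main one: habituation to pictures already seen, or practice with decks already known.

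**Working it through.** **Inputs from the documents.** d = 0.7, two-sided 5%, power 80% (8.2); 20 men in PUK-GHB02 (4.2.2, 4.7.2). **Assumed, because the documents give no value:** the practice gain π, in SDs of the paired difference, and the fraction r of a GHB benefit that persists to the second period.

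**The plan's own figure.** Section 8.2 says "we would need at least 19 subjects to detect significant differences in each experiment". A paired t-test with the noncentral t gives 79.9% at n = 18 and 82.3% at n = 19, so 19 is reproduced. At the planned 20, power is 84.4%.

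**Equal practice gain, balanced sequences.** The expected GHB-minus-placebo difference is D - π in GHB-first men and D + π in placebo-first men. The mean is D, so there is no bias. Without a period term the variance rises from 1 to 1 + π², so the standardised effect is 0.7/√(1 + π²):

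| π | effective d | power, n = 20, no period term | with period term |
|---|---|---|---|
| 0.25 | 0.68 | 82% | 84% |
| 0.5 | 0.63 | 76% | 84% |
| 1.0 | 0.495 | 56% | 84% |

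**Unequal sequences.** If order is decided by coin toss, a split of 13:7 or worse has probability 26%. With π = 0.5 and no period term, the estimate is 0.7 - 0.5 × (13 - 7)/20 = 0.55 when 13 men receive GHB first, and 0.7 + 0.15 = 0.85 when 7 do. A period term restores 0.70 in both cases.

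**Persisting GHB benefit, post-sleep recall as the score.** GHB-first men have period means m + D and m + π + rD; placebo-first men have m and m + π + D. The estimate is ½[(D - π - rD) + (D + π)] = D(1 - r/2).

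| r | d | power, n = 20 | n for 80% |
|---|---|---|---|
| 0 | 0.70 | 84% | 19 |
| 0.25 | 0.61 | 74% | 23 |
| 0.5 | 0.525 | 61% | 31 |

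**Overnight change as the score.** Each night has a recall test before dosing. If the residual rD raises the evening and morning tests equally, it cancels and the estimate is D. If it raises the evening test more than the morning test, the placebo-night change of the GHB-first men is too small and the estimate is too large. Section 4.3.4 defines percentage recalled at both tests but does not say which contrast is analysed.

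**The case against.** The strongest reply is that reuse is implied, not stated. Section 4.3.4 may describe the format of one administration, and 4.3.2 refers to standard procedures. The matching labels on the two nights prove little, since other night-2 entries look copied from night 1: Adaptation Night 2 still lists the first hair sample, although the sample table gives the second. This stands. The text omits parallel forms; it does not rule them out.

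A reader might infer that every learning or picture task has this defect. The documents do not support that. The Multifaceted Empathy Test has no stated item count, the Movie for the Assessment of Social Cognition and the Social Gaze Test have no described item set, and the Learning of Texts and object-location tasks are only named.

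A reader might also infer that the GHB effect is bound to shrink. That needs a post-sleep-only score and an assumed r. The pre-dose recall test makes overnight change a natural score, and there the bias can vanish or reverse. The loss also depends on the assumed effect: at d = 1.2, the top of the range in 8.2, r = 0.5 leaves d = 0.9 and 97% power at n = 20.

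For the scanner SAT, every man has already had one GHB and one placebo day, so earlier exposure is common to both scanner arms. Finally, 8.1 leaves memory out of the primary endpoint, although 4.1 lists it as a primary outcome measure.

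These points limit the claim about direction and size. They do not supply a safeguard: no section gives parallel versions, crossed materials or a period term.

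**Conclusion.** The point holds for four tasks: the paired word list, finger tapping, the gambling task and the SAT. As described, their second session uses material the men have already met, and nothing in the design or the stated analysis deals with it.

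The power loss from an unmodelled practice effect (84% to about 76% or 56%) rests on assumed gains of 0.5 and 1.0 SD. Attenuation to d = 0.61-0.53, with power 74-61%, rests on assumed r = 0.25-0.5, balanced sequences and post-sleep recall as the score. A ceiling in word recall is possible but cannot be quantified. Neither the sign nor the size of any bias follows from the documents. This is a cheap improvement, not a demonstrated bias; if different versions already exist, stating them and how they are balanced settles the materials question.

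**What to change.** - **Section 4.3.4:** specify two parallel word lists and two tapping sequences, crossed with treatment order (version A/B × GHB-first/placebo-first). Change deck positions and pay-offs for the second gambling session. State whether the word-list score is post-sleep recall or overnight change.
- **Section 4.3.2:** use matched SAT picture sets that differ between the two sessions within each crossover pair (days 1+2 and days 3+4), crossed with treatment. A single new set for days 3+4 would not do, because pictures would still repeat within each pair.
- **Section 8.3:** add period to the model. At n = 20 and d = 0.7 this costs almost nothing (84.1% against 84.4% power with no practice effect).
- **Tasks with no parallel form:** report the period-1 comparison as a sensitivity analysis only. With about 10 men per sequence, power is about 32% even if the between-subject d were 0.7 (assumed).

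The cost is preparing second sets and adding a version column to the allocation list. The sets may differ in difficulty, which the crossing balances. Materials cannot be changed once data are collected, so this has to be settled beforehand.
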